5.4 Safety Analysis Set (SAF)

The Safety Analysis Set (SAF) consists of all subjects who enrolled into the study and took at least one dose of study medication.

The SAF will be used for summaries of all safety, tolerability and medication compliance related variables, and subjects will be included based on actual study medication received.

5.5 Biopsy Analysis Set (BAS)

The Biopsy Analysis Dataset (BAS) consists of all mFAS subjects who had at least one post-transplant central pathology assessment.

The Biopsy Analysis Set will be used for summaries of all secondary and exploratory efficacy analyses that need to use central pathology findings.

5.6 Pharmacokinetics Analysis Set (PKAS)

Not applicable

5.7 Pharmacodynamic Analysis Set (PDAS)

Not applicable

6 ANALYSIS VARIABLES

6.1 Efficacy Endpoints

Following the decision from the interim analysis (see Section 7.9), subjects will complete at least one year of study visits, and data analysis will be performed once all subjects complete 12 months of study. Accordingly, efficacy analyses will base on data reported within the one year period.

6.1.1 Primary Efficacy Endpoint(s)

The primary endpoint is a composite endpoint of either the presence of DSA or IA (as assessed by a central lab) on peripheral blood molecular profiling by one year post-transplant.

6.1.2 Secondary Efficacy Endpoints

Comparisons between treatment groups regarding incidence will rely upon assessments for the following results:

- De novo DSA formation over the course of 1 year
 - De novo DSA (positive / negative / indeterminate) up to Day 365
 - Class I and Class II DSA will be assessed by a central HLA lab at 1, 3, 6, 9, and 12 months. Overall, Class I and Class II DSA occurrence (positive / negative) of

the period from transplant to Month 12 will be assessed based on assessments at each visit.

- Endpoints for the subset of DSA positive subjects:
 - initial MFI values and antibody strength (mild, moderate, strong) based on MFI
 - post-transplant peak MFI and antibody strength
 - DSA persistent (yes/no) will be assessed by sponsor based on DSA lab data
 - C1q-binding DSA (positive/negative)
 - DSA IgG3 isotype (positive/negative)

For de novo DSA positive subjects, their initial MFI values and antibody strength, peak MFI and antibody strength, and DSA persistence (yes/no) will be assessed by sponsor based on DSA lab data.

- IA
 - Immune Activation (IA) from Day 1 to Day 365 visit
 - Immune Activation (IA) during the period from Day 30 to Day 365 visit

IA will be regarded as persistent if IA is detected for positivity for any two measurements on or before Day 365 visit.

- TG during the first year

The presence of TG will be reported where TG is defined as $cg > 0$ on centrally-interpreted institutional protocol biopsy or biopsy obtained for cause during the first year post-transplant with +2 months visit window.

- Microcirculatory Inflammation during the first year

The presence of microcirculatory inflammation will be reported where microcirculatory inflammation is defined as $g + ptc \geq 2$ on centrally-interpreted institutional protocol biopsy or biopsy obtained for cause during the first year post-transplant, with +2 months visit window.

- IFTA and Inflammation during the first year

The presence of IFTA and inflammation will be reported where IFTA and inflammation is defined as IFTA positive and inflammation positive ($i > 0$) on centrally-interpreted institutional protocol biopsy or biopsy obtained for cause during the first year post-transplant, with +2 months visit window.

- Thresholds for eGFR

- Values less than 30, 40, and 50 mL/min/1.73 m²

These threshold endpoints will be calculated for months 1, 3, 6, 9, and 12 using the Modification of Diet in Renal Disease (four variable-MDRD) criteria. Assessments are positive or negative.

- Five-point decline in eGFR

The decline in eGFR will be calculated with respect to the eGFR value at Day 30 visit.

- Traditional transplantation composite endpoint

Incidence will be assessed at month 12 for the following:

- Graft loss (defined as retransplantation, transplant nephrectomy, or a return to dialysis for at least a six week duration, or subject death)
- Death
- BPAR – positivity will be determined by local biopsy, central pathology, or reported adverse events.
- Composite occurrence of either graft loss, death, BPAR, and loss-to-follow-up

- Histopathology grading within 1 year

Central histopathology grading over 1 year will be diagnosed according to the BANFF diagnostic categories and subcategories that include the following:

- Normal
- Antibody mediated changes
 - C4d deposition without morphologic evidence of active rejection
 - Acute ABMR (grades: I, II, and III)
 - Chronic active ABMR
 - ABMR: either Acute ABMR or Chronic Active ABMR
- Borderline changes
- TCMR
 - Acute TCMR (grades: IA, IB, IIA, IIB, and III)
 - Chronic active TCMR
- IFTA (grades: I, II, and III)
- Other: all categorical findings will be summarized.
- In addition to the categories above, specimens will be given individual scores for the following: glomerulitis (g), tubulitis (t), intimal arteritis (v), mononuclear cell interstitial inflammation (i), early allograft Glomerulopathy (cg), tubular atrophy (ct), interstitial fibrosis (ci), vascular fibrous intimal thickening (cv), arteriolar hyaline thickening (ah), peritubular capillaries (ptc) and mesangial matrix (mm).

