- Compare the persistence of the development of IA on molecular profiling between two treatment groups across the study duration in those subjects who develop IA on molecular profiling.

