4 SAMPLE SIZE

The sample size for this study was determined based upon a comparison of the rate of the two-part composite endpoint in the Astagraf XL group compared to the immediate-release tacrolimus group. Assuming a rate of 20% would be observed for the immediate-release tacrolimus group compared to a rate of 10% for the Astagraf XL group, 220 subjects per group are needed to achieve an 80% power to detect a difference between Astagraf XL and immediate-release tacrolimus with a two-sided alpha level of 0.05. The study will enroll 275 subjects/group (550 total) to allow for 20% dropout.

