Following secondary endpoints will be summarized with frequencies and percentages by treatment group. The incidence of events will be analyzed for treatment group differences. Analysis of treatment group differences will be implemented from logistic regression model with the same covariates of primary efficacy analysis.

1. De novo DSA formation
2. IA
3. C1q-binding DSA
4. DSA IgG₃ isotype
5. Persistence of DSA
6. Persistence of IA
7. TG (cg $>$ 0)
8. Microcirculatory Inflammation (g+ptc $>$ 2)

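### Persistence of DSA and of IA is compared between arms among patients who became positive, a post-randomisation subset, and for C1q-binding DSA and IgG3 the SAP contradicts itself on the denominator.

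*SAP*

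**What the plan says.** **Persistence.** SAP 6.1.2 opens as a list of between-arm comparisons of incidence. Within it, DSA persistence, C1q-binding DSA and IgG3 isotype stand under "Endpoints for the subset of DSA positive subjects". SAP 3.1.2 compares persistence of IA between the two arms "in those subjects who develop IA on molecular profiling". The last paragraph of protocol 7.4.2 also assesses treatment differences in DSA persistence within the patients who developed DSA and within those who developed IA.

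**C1q-binding DSA and IgG3.** SAP 3.1.2 lists both as one-year incidence comparisons between arms and states no subset. SAP 7.4 puts efficacy on the mFAS, and SAP section 5 defines no DSA-positive or IA-positive analysis set. Protocol 5.3.4 and 5.3.5 have the two assays run in DSA-positive patients.

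**Method.** SAP 7.4.2 places both persistence endpoints, C1q and IgG3 (items 3 to 6) beside de novo DSA and IA. "The incidence of events will be analyzed for treatment group differences", using logistic regression with the primary-analysis covariates, and no denominator is named. SAP 7.1 withholds regression where the event rate is under 10%, which it equates with fewer than 57 subjects. SAP 7.10.1 does not impute missing efficacy endpoints.

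**The concern.** De novo DSA and IA are the two components of the primary endpoint. If Astagraf XL works as hypothesised, it changes who becomes positive, and the positives in the two arms then differ in kind as well as in number. A treatment that mainly prevents weak, short-lived antibody leaves behind a smaller group in which persistent antibody is over-represented. The proportion persistent among positives then rises even if the number of patients with persistent antibody falls. Randomisation does not protect that comparison.

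For C1q and IgG3, the assays are run in positives, missing values are not imputed, and no rule classifies DSA-negative patients. A programmer could therefore arrive at the subset by default, although SAP 3.1.2 and 7.4 indicate the mFAS.

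At stake is the reading of the primary result. Persistence, complement binding and IgG3 are the endpoints a reader would use to judge whether the antibodies prevented were the ones that matter.

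**Working it through.** **The plan's own figure.** SAP section 4 assumes "a rate of 20% would be observed for the immediate-release tacrolimus group" and "a rate of 10% for the Astagraf XL group", and states that "220 subjects per group are needed to achieve an 80% power" "with a two-sided alpha level of 0.05".
- n = [z(0.975)·√(2·0.15·0.85) + z(0.80)·√(0.20·0.80 + 0.10·0.90)]² / 0.10² = 199 per arm, or 219 with continuity correction.
- Fisher's exact test at 220 per arm has 81.1% power, so 220 reproduces.
- 220 / (1 − 0.20) = 275, which matches "275 subjects/group (550 total) to allow for 20% dropout".

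These figures concern the composite endpoint. The documents give no rate for DSA alone or for persistence.

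**Assumptions.** Take 220 per arm as a stand-in for the mFAS. Let every composite event be a DSA event: 20% × 220 = 44 control positives and 10% × 220 = 22 on Astagraf XL. As the lower end of the range, let half of them be DSA: 22 and 11. The persistent counts are also assumed.

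**Formula.** OR (Astagraf XL versus control) = [x_A/(d_A − x_A)] / [x_C/(d_C − x_C)]. Here x is the number of persistent cases and d is either the number of positives or 220.

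| Positives (C, A) | Persistent (C, A) | Among positives | OR | Of 220 per arm | OR |
|---|---|---|---|---|---|
| 44, 22 | 15, 15 | 34.1% v 68.2% | 4.14 | 6.8% v 6.8% | 1.00 |
| 44, 22 | 15, 11 | 34.1% v 50.0% | 1.93 | 6.8% v 5.0% | 0.72 |
| 44, 22 | 22, 11 | 50.0% v 50.0% | 1.00 | 10.0% v 5.0% | 0.47 |
| 22, 11 | 7, 5 | 31.8% v 45.5% | 1.79 | 3.2% v 2.3% | 0.71 |

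Second row in full: (11/11)/(15/29) = 1.93 and (11/209)/(15/205) = 0.72. The direction reverses in rows 2 and 4. In row 3 a halving disappears. In row 1 an absent effect looks like harm. The reversals in rows 2 and 4 are in direction only; none of the comparisons in those rows is statistically significant.

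**Error rate.** In 3,000 simulated trials per setting, DSA incidence was 20% v 10% and persistent DSA was equal in both arms, at a rate between 5.0% and 8.0%. A Fisher test among positives showed significant harm in 47% to 85% of trials. The full-set comparison rejected in 2% to 3%. Fisher's test stands in here for the SAP's logistic model.

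**The 7.1 limit.** With 44 + 22 = 66 positives, 57 events would need 57/66 = 86% of positives to have the endpoint. The table rows have 30, 26, 33 and 12 events, all below 57. As a percentage, 26 events are 26/440 = 5.9% of the full set, which fails the limit, but 26/66 = 39% of the subset, which passes.

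**Persistent IA.** The decision recorded in SAP 7.9 is the branch for a posterior probability of at least 70%. At n = 110, protocol Appendix 12.4 reaches that branch at 25 control events (25/110 = 22.7%, probability 0.737; 24 events give 0.659). That rate is for the composite, and its IA share is not given. Persistent IA would need 57/440 = 13.0% across the two arms to reach the count. That is possible but not established.

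**The case against.** The strongest reply is that the SAP's general rules already point to the mFAS and that 7.1 would suppress most of the testing. Much of this stands.

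- **Are C1q and IgG3 compared only among positives?** A reader of SAP 6.1.2 might infer so. The documents do not settle it: 3.1.2 and 7.4 say one-year incidence in the mFAS, and 7.4.2 names no denominator. The supportable defect is a contradiction. For persistence, SAP 3.1.2 (IA) and SAP 6.1.2 with protocol 7.4.2 (DSA) do name the subset.
- **Would the trial report significant harm?** A reader might infer this from a split such as 22/44 v 20/22 (Fisher p = 0.001, against p = 0.87 for 22/220 v 20/220). The documents do not support that forecast. The splits are assumed, the SAP's method here is logistic regression, and 42 events fall below 57. Since 57 is 10% of 570, close to the 550 planned, the SAP appears to count the whole study. But 7.1 does not say so, persistent IA could pass, and untested percentages among positives mislead in the same way.
- **Is everyone who is not DSA-positive known to be negative?** No. SAP 7.4.1.1 has an indeterminate class (inadequate donor typing) and a missing class (no specimen), so a change of denominator needs a rule for them.
- **Does late onset strengthen the point?** A first positive at Month 12 cannot count as persistent within a one-year analysis. That remains true in the mFAS, so it is a separate limitation of the definition.
- **Context.** These are secondary endpoints in a trial described as exploratory, without multiplicity adjustment. De novo DSA and IA incidence are compared alongside, so a reduction in positives would be visible, and the primary analysis is unaffected.

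**Conclusion.** The concern holds for persistence of DSA and of IA: as written, arms are compared within a subset defined by the outcome under test. For C1q-binding DSA and IgG3 it holds as an inconsistent denominator that must be resolved.

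Under the assumed counts, a 27% reduction in persistent DSA (15 to 11) appears as an odds ratio of 1.93 in the wrong direction among positives, against 0.72 in the full set. A halving (22 to 11) appears as 1.00 against 0.47. The reversal survives halving the number of positives (1.79 against 0.71). Its size depends on assumed positivity and persistence counts; that it can occur does not.

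The practical reach is limited. The 7.1 limit would probably leave the DSA-based endpoints descriptive, with persistent IA the likeliest to be modelled. The point is worth correcting because the subset percentages would still be read as treatment comparisons.

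**What to change.** In SAP 7.4.2 (items 3 to 6), and consistently in 3.1.2 and 6.1.2:

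- Compare persistent DSA, persistent IA, C1q-binding DSA and IgG3 isotype in the mFAS. Count subjects who were tested and negative for DSA (or for IA, for persistent IA) as non-events.
- Handle indeterminate or missing subjects as in the primary analysis: excluded, with negative imputation as the sensitivity analysis. Do not code untested subjects as negative in the main comparison. SAP 7.4.1.1 takes a discontinuation by Day 30 without results as DSA-negative, yet the composite is indeterminate when IA is unknown; say that such subjects are excluded here too.
- Report percentages among DSA-positive or IA-positive subjects as description, without a between-arm test.
- State in 7.1 that the event-rate limit is computed on the mFAS.
- When reporting persistence, note that a first positive at Month 12 cannot qualify.

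The cost is text and programming; the data are already collected. The downside is that several of these endpoints will fall under the 7.1 limit and be descriptive only.

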6.1.3 Exploratory Efficacy Endpoints

Additional exploratory endpoints include the following:

- The validation of peripheral blood molecular profiling will employ the use of a second two-part composite endpoint encompassing the incidence of acquiring DSA or positive evidence of TG on biopsy during the first year post-transplant or by the conclusion of the study.

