The type of antibody reduction therapy will be summarized at each time point using frequencies and percentages. Analysis of treatment group differences will be conducted

using multinomial logistic regression and GEEs with the same covariates used in the primary endpoint's model and random effects(s), as necessary.

Ordinal assessments of antibody strength (weak, moderate, and strong) will be summarized at each time point using frequencies and percentages. Analysis of treatment group differences will be done by time point and overall using a proportional odds model and GEEs with the same covariates used in the primary endpoint's model and random effect(s), as necessary, to account for the temporal structure of data collection.

The continuous endpoint of MFI score will be summarized with descriptive statistics by time point. Due to the expected non-normality of errors, an analysis of treatment group differences will be implemented with a semi-parametric, mixed repeated measures model on rank scores using a random effect of subject and the same covariates included in the analysis of Section [7.4.1.1](#). Least square mean (LS Mean) estimates will be provided at each time point and treatment group differences will be assessed at each time point and overall.

Histopathology assessments will be summarized with both descriptive statistics and frequencies and percentages. Raw biopsy scores, including g, t, v, i, cg, ct, ci, cv, ah, ptc, and mm will be summarized as ordinal outcomes. Analysis of treatment group differences will be performed using the same proportional odds model and GEEs implemented for the analysis of antibody strength. The incidence of binary outcomes including ci, ct, and ptc scores greater than 1 will be summarized with frequencies and percentages. Analysis of treatment group differences will be done consistent with the models using GEEs for the other binary endpoints. For biopsy-based analyses, additional covariates will be added to the existing set in order to account for CIT, WIT, KDPI, DCD status, and the three ex vivo perfusion parameters recorded pre-transplant.

Assessments of association between DSA and IA will be analyzed overall and by treatment group with logistic regression models using DSA formation as the response and IA as predictor.

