7.4.3 Analysis of Exploratory Endpoints

Analysis will be performed on the secondary composite endpoint consisting of DSA formation and the presence of TG ($cg > 0$). The same analysis from Section [7.4.1.1](#) will be conducted for treatment group differences. The analysis will be performed using the mFAS population.

The associations between each of HLA-DQ DSA incidence, ordinal DSA strength, DSA formation, C1q-binding DSA, DSA IgG₃ isotype will be analyzed with respect to each other and with IA, TG, acute and chronic ABMR, histopathology, eGFR at various thresholds (less than 30, 40, and 50 mL/min/1.73 m²), ABMR (acute and chronic), TCMR, graft loss, and mortality. Binary GEE models and proportional odds models will be fit for incidence and ordinal strength of HLA-DQ DSA, respectively. Associations will be analyzed between treatment groups and overall as well as across time points. Analogous methods will be used to assess the association between DSA and each component of the traditional composite endpoint.

The incidence of patients with normal and abnormal creatinine assessments and an IA designation will be summarized with descriptive statistics. Concordance between the IA and biopsy results will be summarized with descriptive statistics for each of the normal and abnormal creatinine assessments. Analysis of concordance between the IA and biopsy results will be conducted using Cohen's Kappa for each of the abnormal and normal creatinine assessments.

Percent MFI reduction will be summarized with descriptive statistics by time point. Analysis of treatment group differences will be done using the same semi-parametric, mixed, repeated measures model implemented for raw MFI scores. MFI shift will be summarized with frequencies and percentages and analyzed for treatment group differences using the same proportional odds model used to analyze DSA antibody strength.

Mapping of expression results to known immunological pathways implicated in immune-mediated, kidney transplant injury will be performed using multiple tools including Gene Ontology, Ingenuity's Pathway Analysis™ (Ingenuity Systems, Redwood, CA), TGI's proprietary tool called ImmuneMap, WikiPathways, GSEA Broad, Panther, and NCBI databases such as DAVID. Visualization of networks and hub genes will be done with Cytoscape. Reports on functional pathway mapping will be prepared and provided to Astellas by TGI.

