3.1.2 Secondary Objectives

The secondary objectives of the study, as stated in the protocol, have been further clarified and adjusted to more closely address the research questions and in consideration of data availability. They are to:

- Assess the risk factors for each of the following outcomes: Interstitial Fibrosis and Tubular Atrophy (IFTA), IFTA and Inflammation, biopsy-proven acute rejection (BPAR), the four-part traditional composite endpoint, early mycophenolate mofetil (MMF) interruption/discontinuation, and estimated glomerular filtration rate (eGFR) status based on three thresholds 30, 40, and 50 at one year.
- Assess and compare, between treatment groups, the association/correlation of the appearance of DSA with the development of IA on molecular profiling at one year.
- Assess and compare, between treatment groups, the incidence of each of the following, occurring over the course of one year : De novo DSA, C1q-binding DSA, DSA IgG₃ isotype, IA, transplant glomerulopathy (TG), select BANFF histology grades (acute and chronic forms of antibody-mediated rejection (ABMR), acute and chronic active T-cell mediated rejection (TCMR), borderline changes, and IFTA), graft loss, mortality, and BPAR.
- Compare, between treatment groups, the incidence of various thresholds of eGFR (less than 30, 40, 50 mL/min/1.73 m²) at Day 365 visit and a five-point decline from Day 30 to Day 365).
- Summarize the distribution of ordinal categories of antibody strength (weak, moderate, strong) between treatment groups across the 1-year study time course.
- Summarize maximum Mean Fluorescence Intensity (MFI) scores by treatment group across the duration of the study.
- Examine histopathology in cases where biopsies were taken for maintenance (up to fourteen months) between treatment groups. In cases where biopsies were performed for cause, they will be examined separately.
- Summarize tacrolimus manufacturer and the number of switches between immediate-release tacrolimus products by the occurrence of study composite endpoint.
- Summarize tacrolimus manufacturer and the number of switches by the status of renal dysfunction.
- Summarize adverse events (AEs) between treatment groups.

- Summarize the absolute and percent changes in eGFR over the study duration beginning from 30 days post-transplant between groups, and in subjects who develop DSA or IA.

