The primary analysis of the treatment group comparison will be based on fitting a multivariable binary logistic regression model with randomized treatment group (Astagraf XL group versus twice-daily, immediate-release tacrolimus group), pre-defined randomization stratification factors (planned use of Campath [Yes/No], levels of KDPI as defined in Section 4.5 of the protocol, and HLA Class II mismatch), recipient age, gender, and race, and pre-transplant cPRA included in the model. Investigational site will be included as a random effect. The limited numbers of subjects per center, however, may make it impracticable to include all sites in the statistical model. If reasonable, data from low enrolling sites (e.g., < 5 subjects) will be combined. The decision to include sites and how to combine sites, if necessary, will be made prior to database unblinding.

Adjusted (common) odds ratio (OR: Astagraf XL group versus immediate-release tacrolimus group) and two-sided exact 95% CI will be provided as measures of strength of association and precision, respectively. The null hypothesis of no treatment effect can be expressed as $H_0: OR = 1$ and will be tested at the ≤ 0.05 level using the Wald's chi-square statistic on one degree of freedom. Odds ratio will also be estimated for the covariates included in the model.

Subjects with primary endpoint unknown, undetermined, or missing will be excluded from the primary analysis.

The hypothesis for the comparison is as follows:

H₀: The proportion of subjects with the primary endpoint is the same between subjects receiving Astagraf XL and subjects receiving immediate-release tacrolimus.

H₁: The proportion of subjects with the primary endpoint is not the same between subjects receiving Astagraf XL and those receiving immediate-release tacrolimus.

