15. BPAR

16. The four-part traditional composite endpoint

Separate risk factor analyses will be conducted for BID Immediate-release Tacrolimus treatment group only. Manufacturer will be included as additional covariate.

Ordinal assessments of antibody peak strength (weak, moderate, and strong) will be summarized based on the results over the course of one year using frequencies and percentages. Analysis of treatment group difference will be done using Fisher's Exact Test.

The continuous endpoint of Peak MFI score will be summarized with descriptive statistics based on the results over the course of one year by antibody.

Histopathology assessments will be summarized with both descriptive statistics and frequencies and percentages. Raw biopsy scores, including g, t, v, i, cg, ct, ci, cv, ah, ptc, and mm will be summarized as ordinal outcomes. Analysis of treatment group differences will be performed using Fisher's Exact Test. The incidence of binary outcomes including ci, ct, and ptc scores greater than 1 will be summarized with frequencies and percentages. Analysis of treatment group differences will be performed using Fisher's Exact test.

Assessments of association between De novo DSA and IA will be analyzed with logistic regression models using DSA formation as the response and IA as predictor using the same covariates detailed in Section 7.4.1.1.

Mean of eGFR by treatment group will be plotted across visits.

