7.4.3 Analysis of Exploratory Endpoints

Analysis will be performed on the secondary composite endpoint consisting of DSA formation and the presence of TG ($cg > 0$). Logistic model with the same covariates of the primary analysis will be conducted for treatment group differences with the incidence of DSA or TG as the response and treatment group as the predictor. The analysis will be performed using the biopsy analysis set.

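### The SAP analysis meant to validate the blood molecular profile does not contain IA, and the protocol's IA-versus-biopsy concordance and by-arm DSA–IA analyses are missing from the SAP

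*SAP*

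**What the plan says.** **Validation claim.** SAP 6.1.3: "The validation of peripheral blood molecular profiling will employ the use of a second two-part composite endpoint encompassing the incidence of acquiring DSA", the second component being TG on biopsy. Protocol 2.3.3 lists the same composite without giving it a validation purpose.

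**Its analysis.** SAP 7.4.3: "Logistic model with the same covariates of the primary analysis will be conducted for treatment group differences with the incidence of DSA or TG". That composite is the dependent variable, and the model is fitted in the biopsy analysis set. The covariates come from SAP 7.4.1.1: the stratification factors, "recipient age, gender, and race, and pre-transplant cPRA included in the model", and site as a random effect.

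**The protocol's direct check.** Protocol 7.4.3: "Analysis of concordance between the IA and biopsy results will be conducted using Cohen's Kappa", separately for abnormal and normal creatinine. The amendment rationale in Protocol Attachment 1 says the assay had been formally validated only in patients with normal renal function.

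**DSA against IA.** SAP 3.1.2 has the objective: "Assess and compare, between treatment groups, the association/correlation of the appearance of DSA with the development of IA on molecular profiling at one year". Protocol 7.4.2 says that the association "will be analyzed overall and by treatment group with logistic regression models using DSA formation as the response and IA as predictor". SAP 7.4.2 fits logistic models "using DSA formation as the response and IA as predictor using the same covariates detailed in Section 7.4.1.1".

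**The concern.** IA alone can make a patient a primary-endpoint event: in the table in SAP 7.4.1.1, a DSA-negative patient with IA present is positive. How a treatment difference is read therefore depends partly on what an IA call means in these patients, including those with abnormal creatinine, for whom the protocol says the assay lacks formal validation. The SAP names one analysis as the validation of that assay. If that analysis cannot bear on the question and the analysis that could has gone, the study report may claim support for IA that the data were never asked to give.

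**Working it through.** The plan gives no figure for this point, so the check sets the passages side by side.

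**1. Does the SAP 7.4.3 model contain IA?** Written out from SAP 7.4.3 and 7.4.1.1:

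logit P(DSA or TG) = α + β·treatment + γ′·(stratification factors, age, gender, race, cPRA) + site

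The SAP describes it as a model "with the incidence of DSA or TG as the response and treatment group as the predictor". IA appears nowhere on either side. Reversing every IA call would leave α, β and γ unchanged, so the fit carries no information about whether IA calls are right.

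**2. What happened to IA against biopsy?**

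| Item | Protocol | SAP |
|---|---|---|
| IA by renal function | Proportion of IA patients with normal and abnormal creatinine (2.1.3) | Proportion with IA by eGFR threshold and creatinine above 1.2 mg/dL (3.1.3) |
| IA–biopsy concordance | Objective in 2.1.3; kappa by creatinine status in 7.4.3 | None |
| Reason for removal | – | Section 8, item 9: a general statement that exploratory analyses were adjusted; concordance not named |

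**3. What IA-to-tissue analysis is left?** SAP 7.4.2 allows IA as the main factor in risk-factor models. Three of the eight outcomes are biopsy-related: IFTA, IFTA with inflammation, and BPAR. Compared with the concordance analysis, these models:
- give adjusted odds ratios, not agreement;
- do not have TG as an outcome;
- are not split by creatinine;
- are subject to SAP 7.1, which bars regression when the event rate is below 10%, stated as fewer than 57 subjects (57 / 0.10 = 570; 10% of the planned 550 is 55).

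**4. Can the SAP 7.4.2 model compare the DSA–IA association between arms?** With the 7.4.1.1 covariates, treatment enters only as a main effect:

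logit P(DSA) = a + b·IA + c·treatment + other covariates

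The IA odds ratio is exp(b) in both arms, so the ratio of the two arms' odds ratios is fixed at 1 by the model. Comparing arms needs separate fits, which the protocol had, or an IA-by-treatment term. The SAP specifies neither.

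**5. Would that model run at all?** DSA is the response, so the 10% rule applies to DSA. The design rates for the whole composite are 20% and 10%, which pool to (20 + 10) / 2 = 15% with equal arms. DSA alone falls below 10% if patients positive on IA only make up more than (15 − 10) / 15 = one third of composite events. The documents do not give the split between DSA and IA, so this shows only that the rule could plausibly apply.

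**The case against.** The strongest reply is that this is one sentence about an exploratory endpoint. The classifier was locked beforehand (Protocol 5.3.8), the SAP discloses that exploratory analyses were adjusted, and the protocol's kappa was itself underspecified: it did not say which biopsy findings count as positive, and biopsies were to be examined only if available. Those points stand, and they limit the weight of the matter. They do not explain why the validation wording stays in 6.1.3. Nor do they cover the DSA–IA comparison, which the SAP keeps as a secondary objective in a list it says was already adjusted for data availability.

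A reader might infer more than the documents support:

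- *That IA is never related to tissue.* The SAP 7.4.2 risk-factor models do relate it to IFTA, IFTA with inflammation, and BPAR. What is missing is agreement, TG, and the split by creatinine.
- *That IA is not compared between arms.* IA and persistence of IA are both on the SAP 7.4.2 list for treatment comparison, and DSA is analysed separately. Only the DSA–IA association by arm is missing.
- *That the two composites would agree misleadingly because both contain DSA.* They would share that component, but neither document plans to compare them within patients. Any kappa for that comparison would rest on assumed rates for an analysis nobody has proposed, so none is given here.
- *That the by-arm comparison is impossible.* The data allow it; the model as written does not provide it.

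**Conclusion.** The point holds as an inconsistency within the SAP and a loss relative to the protocol. The model in SAP 7.4.3 cannot validate molecular profiling, because its result does not depend on IA. The protocol's IA–biopsy kappa by creatinine status is gone without a specific explanation, and the remaining odds-ratio models do not replace it. The between-arm comparison of the DSA–IA association promised in SAP 3.1.2 has no analysis that can deliver it.

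The primary estimate, test and significance level do not change. The effect is on interpretation: how far a difference carried by IA can be taken to reflect immune injury, especially in patients with abnormal creatinine. The conclusion follows from the wording of the two documents and needs no assumed rates. The one-third figure in the working rests on the design rates and equal arms. How precise a restored analysis would be cannot be computed, because the number of biopsied patients is not given.

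**What to change.** 1. **SAP 6.1.3:** delete the validation wording and keep DSA-or-TG as an exploratory endpoint for comparing arms.
2. **SAP 7.4.3:** restore, in the biopsy analysis set, Cohen's kappa of IA against central biopsy findings, separately for normal and abnormal creatinine, with 95% confidence intervals. Include biopsied patients without IA, since agreement cannot be assessed in IA-positive patients alone. State the creatinine definition, which blood sample is paired with the biopsy, and which findings count as positive. Report TCMR, TG and microcirculatory inflammation separately from ABMR, because Protocol 5.3.7 allows DSA to contribute to the ABMR diagnosis. The microcirculatory inflammation cut-off must be settled, since SAP 6.1.2 and 7.4.2 differ (at least 2 against above 2).
3. **SAP 7.4.2:** report the DSA–IA odds ratio in each arm with 95% confidence intervals and a test of homogeneity. If DSA events fall below the 10% regression threshold, use exact 2×2 methods, which that rule does not bar.
4. **SAP section 8:** if the concordance analysis is deliberately not restored, say so and give the reason.

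The cost is SAP wording and two small analyses on data already collected. The downside is precision: with few biopsies or DSA events the intervals will be wide, and the homogeneity test will have little power.
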